12.2.1 Incomplete Start/Stop Dates for Prior/Concomitant Medications/Procedures

Partially missing start/stop dates for prior/concomitant medications and partially missing start dates for prior/concomitant procedures will be imputed in the ADaM dataset for prior/concomitant medications/procedures. However, listings of prior/concomitant medications/procedures the date as is, with missing date components left blank.

For prior/concomitant medications, if the stop date is complete with no missing year, month, or day, and the partially missing start date imputed by the rule below is after the stop date, then the start date will be imputed by the stop date.

Partially missing prior/concomitant medication/procedure start dates will be imputed by the earliest possible date given the non-missing field(s) of the date, if the partial dates are either before or after the date of the first dose of the study drug. Otherwise, they will be imputed with the date of the first study drug dose.

Partially missing prior/concomitant medication stop dates will be imputed by the latest possible date given the non-missing field(s) of the date.

12.3 Analysis Methods for Missing C3G Histological Index of Disease Activity and Disease Chronicity

Primary Analysis Method for Missing C3G Histological Index of Disease Activity and Disease Chronicity at Week 26

The primary imputation model for this study will impute missing Week 26 C3G Histological Index of Disease Activity using Missing at Random (MAR) multiple imputation approach.

The multiple imputation method will be conducted in two parts: PROC MI and PROC MIANALZE.

Multiple imputation will be used to impute missing data and will be implemented using SAS® PROC MI: Missing data may be the result of missing lesion components for calculation of C3G Histological Index of Disease Activity or Disease Chronicity or due to subjects discontinuing the study prior to Week 26 or Week 52. Missing at random (MAR) will be assumed. The primary analysis will be carried out by imputing missing data for the 7 lesions that comprise the Histological Index for Disease Activity and separately for the 4 lesions that comprise the Histological Index for Disease Chronicity. The multiple imputation model will include the two stratification factors (disease type [C3G or DDD] and kidney transplant status [Y/N]), treatment group, in addition values at each visit from baseline through week 26. If the model fails to converge, exclusion of stratification factors may be considered.

For each lesion component, 100 'complete' datasets will be generated using SAS® PROC MI. Imputed individual lesion component scores will then be classified into scale scores (e.g.,

leukocyte infiltration % involvement = 29% would translate to a scale score of 2). The 'complete' datasets for the individual components specific to disease activity and disease chronicity separately, will be merged by imputation number and summed to calculate the Histological Index for Disease Activity and Disease Chronicity and creation of 100 'complete' datasets for evaluation of activity and chronicity scores.

The results from the 100 fitted models will be combined using SAS® PROC MIANALYZE. The estimate of the treatment difference and standard error from the analysis will be analyzed by PROC MIANALYZE to obtain the overall estimate of treatment difference, as well as the confidence interval and p-value for the hypothesis testing. This will be done separately for Histological Index for Disease Activity and Histological Index for Disease Chronicity

The steps to carry out the primary multiple imputation and analysis are described below:

The 6 lesions in disease activity and 2 lesions in disease chronicity with continuous results will be imputed using SAS code below.

```
/* Imputation at Week 26 */
Proc MI Data= num_org Seed= Seedno nimpute= 100
    minimum= . . 0
    maximum= . . 100
    Out= mum_mi26;
    by TRT01PN;
    class DISTYPE RENTRANS;
    var DISTYPE RENTRANS BL W26;
    monotone reg(W26/details) ;
Run;
```

/* Note: In the code above, remove minimum and maximum when imputed value is out of range; replace percentage <0 to be 0 and replace percentage >100 to be 100 for imputed values $^{*/}$

If imputation at Week 52 is explored, code similar to the following will be used.

```
/* Imputation at Week 52 */
Proc MI Data= mum_mi26 Seed= Seedno nimpute= 1
    minimum= . . . 0
    maximum= . . . 100
    Out= mum_mi52;
    by _imputation_ TRT01PN;
    class DISTYPE RENTRANS;
    var DISTYPE RENTRANS BL W26 W52;
    monotone reg(W52/details) ;
Run;
/* Note: In the code above, if the model is not able to be fit, remove Renal
Transplant Status (RENTRANS) */
```

The 1 classification variable in disease activity and 2 classification variables in disease chronicity will be imputed using SAS code below.

```
/* Imputation at Week 26 */
Proc MI Data= cat_org Seed= Seedno nimpute=100
    out= cat_mi26;
    by TRT01PN;
    class DISTYPE RENTRANS BL;
    war DISTYPE RENTRANS BL;
    monotone logistic(W26= DISTYPE RENTRANS BL/ Details Likelihood=AUGMENT) ;
run;
proc sort data= cat_mi26;
    by _imputation_ TRT01PN;
run;
```

If imputation at Week 52 is explored, code similar to the following will be used.

The Summary Statistics, such as Mean and Standard Errors for Imputed dataset are obtained as follows:

```
Note:
    EFFI = Imputed efficacy analysis dataset
    AVAL = Variable analyzed
    Imputation = Imputed number
    TRT01PN = Treatment Group (Placebo/Avacopan)
*** Proc Univariate to generate sample means and standard errors for the variables in
each imputed data set
Proc Univariate Data= EFFI;
     By _Imputation ;
     Class TRT01PN;
     Var AVAL;
     Output Out= SumStat MI
          Mean= AVAL
          Stderr= SAVAL;
Run;
Proc sort data= SumStat MI; By TRT01PN; Run;
*** Proc MIANALYZE;
PROC MIANALYZE DATA = SumStatMI;
     By TRT01PN;
     Modeleffects AVAL;
     Stderr SAVAL;
     ODS Output
          ParameterEstimates = SumStat Mian;
RUN;
```

Note: If variables not requested imputation, the above procedure won't be appropriate. Using PROC MEANS to summary one single imputation to get summary statistics.

The ANCOVA analysis will be carried out using the following:

```
Note:
     EFFI = Imputed efficacy analysis dataset
     Response = CHG/PCHG
     CHG = Change from baseline in C3G Disease Activity or Chronicity
     PCHG = Percent change from baseline in C3G Disease Activity or Chronicity
     Base = Baseline value
     TRT01PN = Treatment Group (Placebo/Avacopan)
*** Perform ANCOVA;
PROC MIXED DATA= EFFI;
     By Imputation ;
     Class TRT01AN(ref='1');
     Model Response = TRT01AN Base / solution cl ddfm = KR
                   residual OUTP = ano_res ;  * studentized residual ;
     Lsmeans TRT01AN / Alpha=0.05 cl diff ;
     ODS Output LSMEANS = ano lsm
                    Diffs = ano diff;
RUN;
*** Combine result;
PROC MIANALYZE DATA = ano lsm;
     By TRT01AN;
     Modeleffects Estimate;
     Stderr;
     ODS Output
           ParameterEstimates = miana_lsm;
RUN;
PROC MIANALYZE DATA = ano diff;
     By TRT01AN;
     Modeleffects Estimate;
     Stderr;
     ODS Output
           ParameterEstimates = miana diff;
RUN;
*** Normality Test;
PROC UNIVARIATE DATA = ano_res Normaltest;
     Class Imputation ;
     Var StudentResid;
     ODS Output
           TestsForNormality = res SW (Where=(Test="Shapiro-Wilk"));
Run;
*** Select the minimum P-value from Shapiro-Wilk test among all imputation;
```

For the primary analysis of change from baseline to Week 26 in C3G Histological Index of Disease Activity and Disease Chronicity, the normality test is performed on the imputed data using the Shapiro-Wilk test where the lowest p-value is selected. If the p-value is < 0.01, normality is rejected, van Elteren's test is used for the treatment comparison. The steps to carry out the analysis are detailed below.

```
Note:
     EFFI = Efficacy Analysis Dataset with multiple imputation
     Response = categorical variable of interest in analysis
     DISTYPE = Disease Type (C3GN or DDD)
     RENTRANS = Renal Transplant Status (Y/N)
     TRT01PN = Treatment Group (Placebo/Avacopan)
*** Van Elteren's Test by each Imputation;
Proc Freq Data= EFFI;
     By Imputation ;
     Table DISTYPE*RENTRANS*TRT01PN*Response / CMH Scores= modridit;
     Ods Output
          CMH= cmh RMS (Where=(AltHypothesis="Row Mean Scores Differ"));
Run;
*** Apply Wilson-Hilferty transformation to the CMH statistic and standardize the
resulting normal variable;
DATA cmh wh;
     SET cmh RMS;
     cmh value wh = ((VALUE/DF)**(1/3) - (1-2/(9*DF)))/SQRT(2/(9*DF));
     cmh sterr wh = 1.0;
RUN;
*** Proc MIANALYZE;
PROC MIANALYZE DATA = cmh wh;
     Modeleffects cmh value wh;
     Stderr cmh_sterr_wh;
     ODS Output
           ParameterEstimates = cmh miana;
RUN;
```

A sensitivity analysis will be performed using a pattern mixture model with multiple imputation for missing data under the missing not at random (MNAR) assumption using the same approach as described for the primary analysis. The steps to carry out the multiple imputation and analysis are described below:

The 6 lesions in disease activity and 2 lesions in disease chronicity with continuous results will be imputed using SAS code below, using the same seed numbers as specified for the primary imputation method.

```
**** Imputation at Week 26, Continuous variable;
Proc MI Data= ERT (Where=(PARAMCD=" ")) Seed= ##### Nimpute= 100
Minimum= . . 0
Maximum= . . 100
OUT= PMMnum_IM26;
Class TRT01PN DISTYPE RENTRANS;
Var DISTYPE RENTRANS BL W26;
Monotone Reg(W26/Details) ;
MNAR Model(W26/ modelobs=(TRT01PN='1')) ;
Run;
```

The 1 classification variable in disease activity and 2 classification variables in disease chronicity will be imputed using SAS code below using the same seed numbers as specified for the primary imputation method.

**** Week 26, Classification variable; Proc MI Data= ERT (Where=(PARAMCD=" ")) Seed= ##### Nimpute= 100 OUT= PMMcat_IM26; Class DISTYPE RENTRANS TRT01PN BL W26; Var DISTYPE RENTRANS TRT01PN BL W26; Monotone Logistic(W26= DISTYPE RENTRANS TRT01AN BL / Details likelihood=AUGMENT); MNAR Model(W26/ modelobs=(TRT01PN='1')) ; Run;

The ANCOVA analysis will be performed as detailed above for the primary imputation method using the imputation datasets.

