2.2.2 Stratification

Subjects will be stratified by elevated or non-elevated levels of C5b-9, and then randomized using a minimization algorithm to receive 30 mg avacopan twice daily or avacopan-matching placebo twice daily for 26 weeks in a double-blind manner:

Both strata, (i.e., C5b-9 levels >244 ng/ml and \leq 244 ng/mL) will include approximately 44 subjects; each level will have approximately 22 subjects randomized (1:1) to the avacopan or avacopan-matching placebo arm, respectively. However, enrollment for the stratum with C5b-9 levels \leq 244 ng/ml could terminate early if subject enrollment in the other stratum (C5b-9 level >244 ng/mL) reaches target enrollment first.

To obtain balance across treatment groups, eligible subjects within each of the C5B-9 level strata will be further stratified based on two factors:

- 1. C3 glomerulonephritis (C3GN) or Dense Deposit Disease (DDD), and
- 2. Whether the subject has received a kidney transplant or not.

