3 STATISTICAL METHODOLOGY

3.1 General Considerations

For efficacy analysis, to control for the Type I error rate, a gate-keeping procedure will be applied for the analysis of the primary efficacy endpoint (percent change in C3G Histologic Index for disease activity). The primary endpoint will be tested in the elevated C5b-9 stratum first with a two-sided $\alpha = 0.05$. If this test reaches statistical significance, then the primary endpoint will be tested in the combined C5b-9 strata (including both elevated and non-elevated C5b-9 strata) with a two-sided $\alpha = 0.05$. If the test in the elevated stratum fails to reach statistical significance, then the test in the combined C5b-9 strata will only be performed as an exploratory analysis. The statistical analysis for the secondary endpoint (C3G Histologic Index for disease chronicity) will be tested at a 0.05 α -level only if the primary endpoint in the same stratum reaches statistical significance.

Data will be summarized descriptively by treatment group as well as separately for the elevated C5b-9 stratum and combined strata. For continuous variables, numbers, means, medians, ranges, standard deviations, and standard error of means will be calculated. Geometric means will be calculated for UACR and urinary MCP-1:creatinine ratio, and other data that are not normally distributed. Frequency counts and percentages will be presented for categorical variables. Listings of raw and derived data will be included as part of an appendix to the CSR.

In analysis tables and listings, the two treatment groups will be referred to as

- 'Placebo', referenced in the protocol as Group A (placebo)
- 'Avacopan', referenced in the protocol as Group B (avacopan)

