5.2 Primary Efficacy Analysis

The primary efficacy endpoint is the percent change from baseline to Week 26 in the C3G Histologic Index for disease activity. The C3G Histologic Index for disease activity can assume a score from 0-21. See Section 2.3.4 for further details on the calculation of C3G Histologic Index for disease activity.

Statistical Hypothesis Testing and Procedure

• The null hypothesis (H0) is that the avacopan group is not different from the placebo group when comparing the percent change from baseline to Week 26 in the C3G Histologic Index for disease activity.

• The alternative hypothesis (H1) is that the avacopan group is different from the placebo group when comparing the percent change from baseline to Week 26 in the C3G Histologic Index for disease activity.

Numbers, means, median, standard deviation, standard error of means, minimum and maximum will be presented by treatment group and study visit. Avacopan and placebo groups will be compared by Analysis of Covariance (ANCOVA) with treatment group as factor and baseline C3G Histologic Index for disease activity as a covariate. The LS mean estimate and corresponding 95% confidence interval (CI) will be estimated for the treatment main effect. The heterogeneity of the treatment effect across disease diagnoses and renal transplant strata may be investigated through subgroup analyses.

As there are no data available to access the possibility of non-normality distribution of percent change or change from baseline, normality distribution tests will be performed for both percent change and change from baseline. It is possible that the normality test would not hold for percent change from baseline or change from baseline or both. In this case, the following is the analysis procedures for the primary efficacy endpoint.

• If the test for normality fails for percent change from baseline at α level of 0.10 but not change from baseline, change from baseline will be used as the primary endpoint;

• If the test for normality fails for both percent change and change from baseline at α level of 0.10, percent change from baseline will be used as the primary endpoint, but non-parametric methodology will be used for the primary endpoint analysis. The van Elteren's test will be applied to test the percent change from baseline endpoint.

The treatment effect based on the baseline complement profile of subjects may also be investigated.

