9 SAMPLE SIZE AND POWER CONSIDERATIONS

A sample size of 22 patients per treatment group (avacopan and placebo, respectively) in each of the C5b-9 level strata is based on the between-treatment difference of -35% in the C3G

Histologic Index for activity at Week 26, standard deviation (SD) 34%, power 90%, and 2-sided $\alpha = 0.05$.

The sample size of 22 per group also provides approximately 90% power to detect a delta of -35% in the C3G Histologic Index for activity between the percent change from baseline in the first 26 weeks and in the second 26 weeks, assuming an SD of 34% for each change. The mean treatment effect size of 35% is considered reasonable based of the following:

- Of the 5 patients with histologic data in the study by Herlitz et al., 2012 with eculizumab, an anti-C5 antibody, 2 patients had a 67% decrease (improvement) in histologic score, 1 had a 43% decrease, and 2 had no change from baseline; the mean decrease for the 5 patients was 35%;
- An improvement in the histologic score of at least 35% is considered clinically meaningful by clinical and histology experts;
- The SD for the percent change from baseline in C3G Histologic Index of activity was 34% in the Herlitz study; a change of 35% of greater will be above the observed variance for this parameter.

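### When normality is rejected for both percent change and change, the primary test moves from baseline-adjusted ANCOVA to a van Elteren test with no baseline term, losing precision and protection against chance baseline imbalance

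*SAP*

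**What the plan says.** SAP Section 5.2 compares the arms by ANCOVA "with treatment group as factor and baseline C3G Histologic Index for disease activity as a covariate". The model statement in Section 12.3 agrees: it contains treatment and the baseline value.

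Section 5.2 then sets out what happens if normality fails, testing at the 0.10 level:

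- Only percent change fails: the endpoint becomes change from baseline, and the baseline-adjusted ANCOVA stays.
- Both fail: percent change remains the endpoint and a rank test takes over. "The van Elteren's test will be applied to test the percent change from baseline endpoint".

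The code for that test in Section 12.3 is "Table DISTYPE*RENTRANS*TRT01PN*Response / CMH Scores= modridit". Disease type and transplant status form the strata. No baseline term, baseline stratum or rank-based adjustment appears there or in Section 5.2.

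Section 12.3 gives a different, single trigger: the lowest Shapiro-Wilk p-value over the imputed datasets falls below 0.01.

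Protocol Section 8.7.5 handles non-normality differently. It adds a CMH test and an ANCOVA on change to the ANCOVA on percent change, and replaces nothing. SAP Section 10 does not list the replacement as a change from the protocol.

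**The concern.** The confirmatory p-value in the elevated C5b-9 stratum can come from an analysis that ignores the one covariate the plan chose for its main model. Nothing in the design covers the gap: minimisation uses disease type and transplant status within C5b-9 stratum (Protocol Section 3.1, SAP Section 2.2.2), not baseline activity. Dividing by baseline is not covariate adjustment either, because regression to the mean usually leaves percent change correlated with baseline. Baseline values in the imputation model affect only patients with missing data.

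At stake are some power and, with about 44 patients, a treatment contrast that carries any chance difference in baseline activity. Section 5.2 says that no data are available to judge non-normality, so the branch could be reached.

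**Working it through.** **Inputs from the documents.** SAP Section 9: "A sample size of 22 patients per treatment group (avacopan and placebo, respectively) in each of the C5b-9 level strata"; a "between-treatment difference of -35% in the C3G" Histologic Index; "standard deviation (SD) 34%, power 90%, and 2-sided" alpha 0.05.

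**Assumed, not in the documents.** Within-arm correlation rho between baseline and percent change of 0 to 0.5; strata of 14/4/3/1 patients per arm; complete data; standardised exponential errors, since the fallback runs only under non-normality. As an illustration of rho, a 0-21 score with no treatment effect and a baseline-to-follow-up correlation of 0.4 to 0.8 gave a rank correlation of percent change with baseline of about -0.5 to -0.3. The sign does not affect the simulation, because simulated baseline is symmetric.

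**Step 1: the plan's own figure.** n per arm = 2(1.960 + 1.282)² × 34² / 35² = 2 × 10.51 × 0.944 = 19.8, so 20. The exact t calculation needs 21 (power 0.902), and 22 gives 0.915. The plan's 22 is reproduced by an unadjusted two-sample comparison.

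**Step 2: power.** Response = 34 × (rho × baseline + √(1 − rho²) × error) − difference × treatment, 4,000 trials per cell. The adjusted test takes modified ridits of response and baseline within strata, removes one pooled slope and runs the same CMH row-mean-score test on the residuals.

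| Difference | rho | ANCOVA | van Elteren | Rank ANCOVA | Gain over van Elteren (points) |
|---|---|---|---|---|---|
| 35 | 0 | 0.895 | 0.973 | 0.968 | -0.5 |
| 35 | 0.3 | 0.920 | 0.967 | 0.972 | 0.5 |
| 35 | 0.5 | 0.953 | 0.947 | 0.980 | 3.3 |
| 25 | 0 | 0.676 | 0.860 | 0.849 | -1.1 |
| 25 | 0.3 | 0.702 | 0.801 | 0.828 | 2.7 |
| 25 | 0.5 | 0.782 | 0.725 | 0.839 | 11.4 |

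Monte Carlo error on a single power is about 0.3 to 0.7 points. A separate run put the planned difference at rho 0.5 at 0.955 against 0.985, again 3 points. With no treatment effect, rejection was 0.043 to 0.054 for both rank tests.

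**Step 3: chance imbalance.** The difference in baseline means has standard error √(2/22) = 0.30 baseline SD, so P(|difference| > 0.3 SD) = P(|Z| > 0.995) = 0.32. At rho 0.5, an imbalance of 0.30 SD shifts the unadjusted contrast by 0.5 × 34 × 0.30 = 5.1 points, and 5.1/35 = 15% of the planned effect. Within those imbalanced trials, at rho 0.5 with skewed errors, van Elteren's type I error was about 0.09 to 0.12 across runs with different seeds and skewed shapes. The baseline-adjusted rank test stayed at about 0.04 to 0.05.

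**The case against.** The strongest reply is that the switch may help. With skewed errors and the planned difference, van Elteren has power 0.97 against 0.90 for ANCOVA at rho 0. In an illustrative simulation of rounded 0-21 scores it beat ANCOVA in all six settings. In the settings where the SD of percent change was nearest the planned 34 (about 28 to 44), rank ANCOVA added only 0 to 3 points. This stands: it argues for keeping ranks and adding baseline to them.

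A baseline-adjusted ANCOVA is also fitted before the normality test, which uses its residuals, and is specified for the completer and pattern-mixture analyses. An imbalance would therefore be visible, although none of these supplies the confirmatory p-value.

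Four stronger readings are tempting and are not supported:

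- **The fallback is invalid.** Averaged over randomisations, type I error is about 0.05. The excess is conditional on imbalance.
- **The planned power depended on the covariate.** Step 1 shows that it did not.
- **Any rejection of normality loses baseline.** Under Section 5.2 this needs both measures to fail.
- **The gain is 5 points or more at the planned effect.** Normal errors at rho 0.5 give that (0.886 to 0.936), but the fallback is meant for non-normal data.

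Chronicity follows the same route and has the same omission. Its SAP endpoint is change, so the argument from dividing by baseline does not carry over, and no gain was quantified.

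**Conclusion.** The point holds as a matter of efficiency and robustness to imbalance; the validity of the test is not in question. On the van Elteren branch the primary comparison drops baseline activity, and the design does not balance it. With skewed errors, adding baseline to the rank test is worth about 0 to 1 point of power at rho 0 to 0.3 and about 3 points at rho 0.5 if the planned difference is met. If the true difference is 25, it is worth about 2 to 3 points at rho 0.3 and 11 at rho 0.5. The shortfall case matters because the planned effect rests on five patients in an external eculizumab study. The protection against imbalance applies to about a third of trials if rho is near 0.5.

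These sizes rest on the assumed correlation, error shape and strata, and on the planned 22 per arm. How often the branch is reached is unclear while Sections 5.2 and 12.3 state different triggers. The change is worth making because it is nearly free.

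**What to change.** Before unblinding, name a stratified rank ANCOVA as the non-parametric fallback in SAP Sections 5.2 and 12.3:

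1. Within disease type by transplant status, take modified ridits of the response and of the baseline index.
2. Regress response ridits on baseline ridits with one pooled slope.
3. Run the CMH row-mean-score test on the residuals in each imputed dataset.

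State in advance how sparse strata are pooled; SAP Section 5.1 already allows low-count groups to be combined. Report the unadjusted van Elteren test and the baseline-adjusted ANCOVA as supportive, which restores the protocol's practice of reporting both kinds of analysis. State one trigger in both sections, and list the change in SAP Section 10. Apply the same specification to chronicity, with its own baseline index.

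The cost is SAP wording and a few lines of SAS, with no new data. The statistical downside is about one point of power if baseline is unrelated to response (0.860 to 0.849 in the table).

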The SAS code to generate the Analysis of Covariance will be similar to the following:

See Appendix 12.3 for the SAS code to perform van Elteren's test to compare the two treatment groups using the imputed datasets.

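### SAP 5.2 and Appendix 12.3 give conflicting triggers for the non-parametric primary test, and its pooling step names no tail, so its level is about 0.026 or 0.053 instead of a defined 0.05

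*SAP*

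**What the plan says.** **Level and gate.** SAP 3.1: "The primary endpoint will be tested in the elevated C5b-9 stratum first with a two-sided" alpha of 0.05. Success there opens the test in the combined strata. The chronicity index is tested only if the primary endpoint succeeds in the same stratum. SAP 5.2 words the alternative as a difference in either direction.

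**Trigger in SAP 5.2.** Percent change and change are both tested for normality at 0.10. If percent change fails "but not change from baseline, change from baseline will be used as the primary endpoint". In the other branch, where the "test for normality fails for both percent change and change from baseline", percent change stays the endpoint and van Elteren's test replaces ANCOVA. For the code, 5.2 refers to Appendix 12.3, which is to supply the "test to compare the two treatment groups using the imputed datasets".

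**Trigger in Appendix 12.3.** In a sentence about change from baseline to Week 26, the lowest Shapiro-Wilk p-value on the imputed data is taken. "If the p-value is < 0.01, normality is rejected" and van Elteren's test is used.

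**Pooling in Appendix 12.3.** "The steps to carry out the analysis are detailed below". For each imputation, the code takes the row-mean-scores CMH chi-square (modified ridit scores, stratified by disease type and transplant status) and applies a Wilson-Hilferty cube-root transformation, "cmh value wh = ((VALUE/DF)(1/3) - (1-2/(9*DF)))/SQRT(2/(9*DF". It sets the standard error to 1.0, passes the result to PROC MIANALYZE with "Modeleffects cmh value wh", and ends at the parameter-estimates table. Neither the code nor the surrounding text says which tail gives the p-value.

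**The concern.** When normality is rejected, van Elteren's test is the primary test and therefore also the gate to the combined-strata and chronicity tests. Two things about it are not settled.

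First, the two sections disagree on when it applies. A programmer following 5.2 and one following 12.3 can run different primary tests on the same data.

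Second, with two arms the statistic taken from each imputation is an unsigned chi-square on one degree of freedom, and only large values speak against the null hypothesis. After transformation, small values become negative. A two-sided p-value then spends half its alpha on a tail that carries no evidence, so the test no longer has the level that SAP 3.1 sets. Since no tail is named, the reported p-value depends on a choice that the plan does not make.

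**Working it through.** **1. The two triggers side by side**

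| | SAP 5.2 | Appendix 12.3 |
|---|---|---|
| Threshold | 0.10 | 0.01 |
| Scale | percent change and change | sentence names change from baseline |
| p-value over imputations | not stated | lowest |
| Only percent change fails | endpoint becomes change | no such branch |
| van Elteren used when | both scales fail | lowest p is below the threshold |

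Take complete data, so that each scale has a single p-value, and let it be 0.05 on both.
- 5.2: 0.05 < 0.10 on both scales, so van Elteren's test on percent change.
- 12.3: 0.05 is not below 0.01, so ANCOVA stays.

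The same split occurs for any pair of p-values that both lie between 0.01 and 0.10.

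**2. Level of the pooled statistic with complete data**

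Inputs: two-sided alpha 0.05 (SAP 3.1), DF = 1 (two arms), standard error 1.0 and the transformation (Appendix 12.3).

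Plan's own figure: the untransformed chi-square X has critical value 3.841 and level 0.05.

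At DF = 1 the code computes W = (X^(1/3) − 7/9) / √(2/9), where 7/9 = 0.7778 and √(2/9) = 0.4714.

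- Smallest W (X = 0): −0.7778 / 0.4714 = −1.650. This is above −1.96, so the lower tail can never reject.
- Two-sided reading: reject if X > (0.7778 + 1.960 × 0.4714)³ = 1.7017³ = 4.928. P(χ²₁ > 4.928) = 0.0264.
- Upper-tail reading: reject if X > (0.7778 + 1.645 × 0.4714)³ = 1.5532³ = 3.747. P(χ²₁ > 3.747) = 0.0529.

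| X | chi-square p | W | two-sided p on W | upper-tail p on W |
|---|---|---|---|---|
| 3.841 | 0.050 | 1.672 | 0.094 | 0.047 |
| 4.5 | 0.034 | 1.852 | 0.064 | 0.032 |

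With complete data, a chi-square between 3.75 and 4.93 passes under one reading and fails under the other. The two-sided p-value does not even order the evidence correctly. At X = 0 (no difference at all) it is 0.099, while at X = (7/9)³ = 0.47, where W = 0, it is 1.

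**3. Level with missing data (simulation, 100 imputations, Rubin's rules)**

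The missing-data rates and models below are assumptions; the SAP gives none.

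- *Data-level model:* 22 per arm, four strata of 26/6/8/4, integer scores, baseline mean 8 and SD 3, Week 26 residual SD 2.7, values missing completely at random, total score imputed by arm. At 0/10/20/30% missing, the two-sided level is 0.025/0.024/0.020/0.020 (simulation SE 0.001 to 0.002) and the upper-tail level is 0.052/0.050/0.044/0.041.
- *Idealised normal model:* the two-sided level is 0.026 to 0.028 up to 40% missing information and 0.030 at 50%. The upper-tail level is 0.051 to 0.057.
- *Signed z pooled instead:* 0.048 to 0.051 in the idealised model at 0 to 50% missing information. A further data-level simulation (22 per arm, two strata of 16 and 6 per arm, normal or heavy-tailed or skewed errors) gave 0.050 to 0.053 with none missing and 0.037 to 0.047 with 10 to 20% missing.

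**The case against.** **On the trigger.** The 12.3 code defines the response as either change or percent change, so its normality check could be run on each scale as 5.2 requires, and the 12.3 sentence may be only a loose summary. That is fair as to scale. It does not make 0.10 and 0.01 agree. A reader might also infer that the two rules give different tests when percent change fails clearly and change does not. The text does not support this: the 12.3 sentence speaks of change from baseline, so if change passes, both sections lead to ANCOVA.

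**On the tail.** The upper tail of a one-degree-of-freedom chi-square already is the two-sided comparison of two arms. Read that way, the code has a level of about 0.053, close to what SAP 3.1 asks, and one sentence would settle the matter. This stands: the 0.026 is conditional. The two-sided reading is still the natural one, because 3.1 calls for a two-sided test and the general pooling text in 12.3 takes the p-value from PROC MIANALYZE. That text describes the estimated treatment difference and its standard error, however, so it does not decide the question for van Elteren's test.

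**On the source.** Some code that the SAP announces is absent from the text as read from PDF, so a later step cannot be ruled out. The van Elteren block itself looks complete, and the trigger conflict is in prose.

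**On consequence.** ANCOVA is the planned primary analysis, and the likely error is conservative. Both points are correct and limit the weight of the concern.

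**Conclusion.** Both parts hold and should be fixed before unblinding.

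1. The triggers contradict each other on the threshold, the condition and the endpoint switch, and this can change which primary test is run.
2. The pooling step does not define a test at the stated level. With complete data the level is 0.026 if a two-sided p-value is taken and 0.053 if the upper tail is taken. With missing data the two-sided level stays at about 0.02 to 0.03, depending on the assumed model.

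The complete-data figures rest on the large-sample chi-square distribution. The missing-data figures rest on the simulation assumptions given.

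Three stronger readings are tempting and not supported:
- *The level is 0.026 or lower.* The tail is not stated, and one missing-data model gives up to 0.030.
- *Type I error is seriously inflated.* The two-sided reading is conservative, and the upper-tail reading exceeds 0.05 by only about 0.003 with complete data.
- *A definite loss of power, or a definite frequency of the trigger conflict.* Either figure needs an outcome distribution, and SAP 5.2 itself says there are no data on which to judge normality.

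**What to change.** **Trigger.** Replace the 0.10 rule in 5.2 and the 0.01 rule in 12.3 with one rule, fixed before unblinding. It should state the scale or scales tested, one threshold, how the p-value is taken over the imputations, and the endpoint and test that follow from each outcome.

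**Pooling.** Preferably, pool the signed van Elteren z from each imputation: the square root of the chi-square with the sign of the stratified rank-score difference, standard error 1. Report the two-sided p-value. This also gives the direction of effect, which the present statistic lacks. Alternatively, keep the transformation and state that the upper-tail p-value of the pooled quantity is used, noting a level of about 0.053 without missing data.

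**Cost.** A few lines of SAS (the CMH chi-square carries no sign, so the direction must be output as well) and two or three SAP sentences. SAP section 1 allows revision of the primary analysis before database lock or snapshot. No new data are needed.
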